**C.2.7.2 Smartphone application:** We will use a commercial sleep tracking application to provide participants feedback on their sleep behaviors. Participants will download the Fitbit smartphone application on their smartphone and participate in a brief training in the intervention orientation session. Participants will be trained to review and edit their Fitbit sleep log each day, thus increasing the validity of the data. Although the Fitbit application has developed the ability to enter sleep goals, these features will not be set on participants' applications. In addition, participants will be able to use other features (e.g. step goals) but not trained or instructed on the use of these application features as part of the intervention.

**C.2.7.3 Intervention content (Figure 4):** Participants will receive automated content including didactic lessons for 8 of the 12 weeks with gap weeks included for participants to work on behavior change beginning at Week 5 (see schedule Table 5), individualized progress reports (weekly), and bedtime reminder text messages. The intervention content was developed by psychologists with advanced training in sleep and behavior change (Drs. [name] and [name]) and has been piloted in initial user testing. The 8 didactic lessons (estimated duration 8-10 min) of written and video didactic content will be delivered via email using REDCap and can be viewed on smartphone, desktop, or tablet. Content from the lessons will be reinforced in the telephone coaching sessions. Participants will receive an automatically generated report each week detailing their days of device usage, average bedtime, wake time, sleep duration, and an encouraging statement linked to the weekly didactic content. Participants will also receive a bedtime reminder via text message via their smartphone 30 min before their scheduled bedtime. They can disable the text reminder for Weeks 7-12.

[figure not shown]

Figure 4. Didactic lessons will be sent weekly to intervention participants via ..

**Table 5.** Intervention Didactic Content and Coaching Schedule

Week	Content – Sleep-Opt	Content – Healthy Living	Coaching
1	Intro Basics of Sleep: 
 
• Why do we sleep?
 
• How much sleep is recommended?
 
• Consequences of poor sleep with diabetes
 
	Introduction to health living; dental health	20 min engagement session

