**C.2.7.4 Coaching:** All participants will be assigned to an interventionist who will be a sleep coach to monitor their progress during the study and provide telephone coaching sessions related to their sleep-related goals. Coaches will be recruited, trained, and supervised by [name]. The coaching protocol developed by [name] is based on the principles of Supportive Accountability. The coaches will establish **legitimacy** by their knowledge of sleep and basic counseling principles. They will establish **goals** with the participants based on the participants' values and beliefs, including the sleep-related goals and usage goals (e.g., number of days wearing the sleep tracker). **Performance monitoring** will be completed through an online dashboard visible to the coaches (Fitabase®). The dashboard will contain data from sleep diaries and the wearable sleep tracker. The first coaching session will be a 20-min engagement session, which includes introductions, rationale for the program, clarifying roles of the coach, and the participants' goals for the program. Coaches (directed by [name]) will provide feedback to the participant based on wearable sleep tracker data. For subsequent coaching sessions, the coach and participant will also have weekly brief (5-10 min) follow-up support calls to troubleshoot any problems with the application or wearable sleep tracker, review progress, problem solve barriers to progress, and set goals. Between sessions, the coaches will be available, mostly via email to troubleshoot any problems with the application or wearable sleep tracker. All coaching sessions, text and email communication will be recorded, and a selection of sessions will be coded for intervention fidelity. The use of coaching has been demonstrated to improve adherence to technology-based interventions. [name] has extensive experience in the use of coaching to improve adherence to technology-based interventions.

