**C.2.8 Healthy Living Attention Control.** The research will be conducted remotely by phone call/video conference (Zoom) at participants' preference. The design of the 12-week control group is intended to control for the coach contact in the intervention group, so that we can test the intervention-related components (e.g. motivational enhancement, goal setting, feedback, and sleep education). [name] will train and oversee the coaches for the attention control group. Participants assigned to the health education control group will be provided eight scheduled emails with health education content (e.g. cooking, handwashing, stretching exercises; 8-10 minutes in length) with content written at the 4th grade level or below. Participants will receive eight brief (5- 10 min) telephone contact from the coach (see schedule Table 5) to determine if they received the information and if they had any questions about the materials. The schedule will mirror that of the intervention group. Coaches will not provide counseling or goal setting but may clarify terms or concepts. Participants in the healthy living control group will be instructed not to change their sleep behavior. They will be eligible to receive the sleep intervention at the end of the study. After the final follow-up session, they will receive a Fitbit wearable fitness tracker.

**C.2.9 Measures.** Self-report questionnaires will be used to obtain demographic, literacy, health information, menopausal status, food intake, psychological, behavioral and self-management characteristics (Table 6).

**C.2.9a Primary outcome and additional glycemic measures: Glycemic assessment.** 1.) Glycemic control will be assessed using hemoglobin A1C (A1C; Home Access Health Corp/Everlywell). A1C is a gold standard marker of glycemic control in T1D reflecting average glucose levels in the previous 90 days. 2) **Glycemic variability using CGM (blinded)** will be conducted using FreeStyle Libre Pro glucose sensor or Dexcom (FDA-approved). The sensor tracks glucose concentrations in the interstitial fluid over 24 h using a thin flexible filament (< 0.4 mm thick) inserted into the upper arm (5 mm depth). The system captures glucose levels every 1 minute and records the data every 15 minutes. Variables we will derive from the CGM are mean glucose level, standard deviation (SD), coefficient of variation (CV), percentage of time spent in range (70-180

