mg/dL), percentage of time < 70 mg/dL, and percentage of time spent  $\geq 180$  mg/dL. Interstitial glucose measurements with FreeStyle Libre and Dexcom were found to be accurate compared with capillary blood glucose reference values with a mean absolute relative difference (MARD) of 12% and 9% respectively compared to the gold standard YSI measure of blood glucose. Accuracy of 10% MARD have been approved for self-adjustment of insulin doses in clinical practice. Glycemic measures will be obtained for one week at baseline and Weeks 6, 12, and 24. In our pilot study we experienced a 10% sensor failure rate (less than 15% failure rate reported by the manufacturer and may be due to the team's expertise in placing these devices). Most sensor failure was due to dislodgement. If dislodgement occurs, we will overnight mail a new sensor to the study participant. The dislodged sensor retains the recorded data. Participants will be instructed to return the sensor. We anticipate a 24-hour disruption in data collection with dislodgement.

**C.2.9b Wrist actigraphy to measure behavioral sleep** Participants will wear an Actiwatch Spectrum Plus (Respironics, USA) on their non-dominant wrist for one week during baseline assessment, and Weeks 6, 12 and 24. Data will be collected in 30-sec epochs. Actiwatch records activity, light exposure, and wear time. Subjects will be asked to keep a daily sleep log and press an event marker on the Actiwatch at bedtime and wake-up time. Data will be downloaded and reviewed with each participant to clarify inconsistencies when the Actiwatch is returned. Rest intervals will be set using reported try-to-fall-asleep times and wake-up times on daily sleep logs or event markers if these times are missing. Using the Immobile Minutes algorithm in the Actiware 6 software, we will derive the following variables: sleep onset, sleep offset, sleep duration, sleep efficiency (a measure of sleep quality), mid-sleep time (time point between sleep onset and wake time), and standard deviation (SD) of sleep duration, an indicator of sleep variability which we previously showed to be related to glucose metabolism.

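### Actigraphy scoring windows for two of the three primary outcomes come first from the participant's own sleep log, which the arms complete under different conditions after randomisation; the plan neither guards against this nor tests it

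*Combined protocol and SAP*

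**What the plan says.** C.2.9b describes the measurement. Both arms follow the same procedure for one week at baseline and at Weeks 6, 12 and 24: "Subjects will be asked to keep a daily sleep log and press an event marker on the Actiwatch at bedtime and wake-up time". The scoring window is then fixed as follows: "Rest intervals will be set using reported try-to-fall-asleep times and wake-up times on daily sleep logs"; the event marker serves only where the log gives no times. Sleep within the window is decided by software: "Using the Immobile Minutes algorithm in the Actiware 6 software, we will derive the following variables"; these variables include sleep duration and its SD. There is also a manual step: "Data will be downloaded and reviewed with each participant to clarify inconsistencies when the Actiwatch is returned". No rule says when that conversation may change a window. C.2.6.1 shows that the log is a paper form mailed with the Actiwatch. Table 6 lists these measures as objective and gives the diary a confirming role.

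Conditions after randomisation differ by arm:

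- **Sleep-Opt.** Participants receive a Fitbit (C.2.7.1). On its log, C.2.7.2 says: "Participants will be trained to review and edit their Fitbit sleep log each day, thus increasing the validity of the data". They also receive weekly reports of bedtime, wake time and duration, and a bedtime text that they can switch off for Weeks 7 to 12 (C.2.7.3). A coach sets sleep goals with them, and of the coach's display C.2.7.4 says: "The dashboard will contain data from sleep diaries and the wearable sleep tracker". The stated goal is a change of at least 30 minutes in variability and/or sleep time (C.2.7).
- **Control.** Coaches set no goals, and participants are told not to change their sleep. On the tracker, C.2.8 says: "After the final follow-up session, they will receive a Fitbit wearable fitness tracker".

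C.2.7.4 opens by giving all participants a sleep coach. It sits within the Sleep-Opt section, however, and C.2.8 describes a different coach for controls.

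**The concern.** The outcome is treated as objective, but a participant who knows which programme they are in writes down the limits of each scored night. At baseline neither arm has the trial's Fitbit, goals or coaching, so logs are kept under equal conditions. At Weeks 6 and 12 they are not. A Sleep-Opt participant has a tracker record to copy from and a target to write towards. Any resulting shift falls only on post-randomisation values, so including the baseline value in the model does not correct it.

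A between-arm difference in sleep duration or SD could then partly reflect how the log was filled in. The same measures are the mediators in the revised Aim 3 path models, so an artefact would carry into those as well. C.2.7.1 prefers actigraphy because consumer trackers are less precise; with log-first windows and no instruction against copying, tracker times can still enter the primary outcome.

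**Working it through.** **Inputs.** From C.2.5: 60 per arm after attrition, two-sided alpha 0.02, 80% power, SD 49 min (duration) and 30 min (variability), correlation between time points 0.5 to 0.8 (pilot 0.56 to 0.85). From Table 4: duration 355 vs 380, variability 75 vs 57. From C.2.10 and the Addendum: analysis alpha 0.05. The documents give no figure for log error or for a reporting shift by arm; every bias size below is an assumption.

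**Step 1: reproduce the plan's figure.** For a two-group pre-post change,

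MDD = SD × √(2(1−r)) × √(2/60) × (z₀.₉₉ + z₀.₈₀), with √(2/60) = 0.1826 and 2.326 + 0.842 = 3.168.

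- r = 0.5: 1.000 × 0.1826 × 3.168 = 0.578 SD
- r = 0.8: 0.632 × 0.1826 × 3.168 = 0.366 SD

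These round to the stated 0.6 and 0.4 SD. The Table 4 differences are 380 − 355 = 25 min (25/49 = 0.51 SD) and 75 − 57 = 18 min (18/30 = 0.60 SD).

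**Step 2: compare an assumed shift with the target.** If one arm's window is 5 to 15 min longer per night and all of it is scored as sleep (an upper bound), the share of the duration target is 5/25 = 20% to 15/25 = 60%.

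**Step 3: how often bias alone would look like an effect.** With no true change in sleep, SE = SD × √(2(1−r)) × √(2/60) and the chance of a significant result from bias b is Φ(b/SE − z) + Φ(−b/SE − z). At r = 0.56, SE = 49 × 0.938 × 0.1826 = 8.39 min for duration and 30 × 0.938 × 0.1826 = 5.14 min for variability.

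| Assumed bias | r = 0.56, alpha 0.05 | r = 0.56, alpha 0.02 | r = 0.85, alpha 0.05 |
|---|---|---|---|
| Duration 5 min | 9.2% | 4.4% | 17.5% |
| Duration 10 min | 22.2% | 12.8% | 53.2% |
| Duration 15 min | 43.2% | 29.5% | 86.5% |
| Variability 2 min | 6.8% | 3.0% | 10.2% |
| Variability 5 min | 16.4% | 8.8% | 38.5% |
| Variability 10 min | 49.5% | 35.2% | 91.5% |

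The Addendum reports credible intervals, so read these as approximate chances that the interval excludes zero.

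**Step 4: direction.** A simulation gave both arms identical true sleep (7 nights, mean 355 min, nightly SD 75 min) and varied only the log. Control logs had an error SD of 15 min at each end, and 0 to 50% of quiet wake was scored as sleep (all assumed).

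| Sleep-Opt log behaviour | Measured duration | Measured SD |
|---|---|---|
| More accurate (error SD 0) | +4 to +7 min | −0.6 to −1.4 min |
| Window 10 min wider at each end | +5 to +13 min | almost unchanged |
| Window 20 min wider at each end | +6 to +24 min | almost unchanged |
| Pulled 25% toward a fixed schedule | −2 to −4 min | −6 to −12 min |
| Pulled 50% toward a fixed schedule | −5 to −11 min | −13 to −24 min |

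No single behaviour materially improves both outcomes. Wider windows help duration; regularised logs help SD but reduce duration.

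**Step 5: look for a safeguard.** C.2.6.1 conceals allocation from personnel other than the project director and the investigators overseeing the arms, but does not name the actigraphy scorers. Nothing tells participants not to copy Fitbit times. The sensitivity analyses in C.2.10 and the Addendum address baseline imbalance and missing data; none changes the scoring window.

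**The case against.** The case for the plan has real weight. The log only bounds the window and the algorithm decides what is sleep inside it. Both arms use the same log and marker. The Actiwatch also records activity and light, and review against the recording could expose logs that are too tidy. There is a general concealment statement. These points limit the effect but do not remove it: participants know their programme, scorers are not named, and the review has no written rule.

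Some stronger readings are tempting, and the documents do not support them.

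- A reader might infer that every such error favours Sleep-Opt. Step 4 shows otherwise: logs pulled toward a schedule lower SD and also lower measured duration.
- A reader might infer that coaches watch the log that defines the outcome. The coach's dashboard holds sleep diaries, but nothing says that the paper log is one of them, and C.2.7.4 bases coach feedback on tracker data.
- A reader might infer that bedtime texts shape the Week 12 log. Participants can disable them in Weeks 7 to 12.
- A reader might infer that controls write from memory. Nothing stops a control from using a tracker already owned; the documented asymmetry is in what the trial supplies.
- A reader might conclude that event markers should replace the log. The marker is also operated by the participant, and it is pressed at bedtime, whereas the log asks for the time of trying to fall asleep. Marker-first windows could add quiet wake in bed, so the change is a trade-off and not a clear gain.

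**Conclusion.** The concern holds as a possibility that the plan leaves open, not as a demonstrated bias. Two of the three primary outcomes rest on windows set first by the participant's log, and the conditions for keeping that log differ by arm only after randomisation. Baseline adjustment does not remove a resulting shift, and no planned analysis would reveal it.

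The size is unknown. If 5 to 15 minutes were added and fully scored as sleep, that would be 20% to 60% of the Table 4 duration difference; at r = 0.56 and alpha 0.05 it would produce a significant result in about 9% to 43% of trials with no change in sleep. For variability, a material shift needs logs regularised toward a schedule, since better accuracy alone moves SD by under 2 minutes. The direction may differ between the two outcomes. Exposure at Week 24 is probably smaller, because coaching has ended and what remains is the retained Fitbit and earlier training. A1C does not depend on the scoring window.

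**What to change.** Keep log-first scoring as the primary rule and add three things to C.2.9b, with the analysis in (c) also entered in the Statistical Analysis Addendum:

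- **(a)** Instruct participants to complete the paper log without consulting or copying Fitbit or app times.
- **(b)** State that staff blinded to allocation score and lock each recording before any review with the participant, and that later changes are logged with a reason.
- **(c)** Pre-specify a sensitivity analysis of Week 12 sleep duration and SD using the software's automatic rest intervals, with no log input, and report log-minus-marker times by arm.

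The cost is some wording and some rescoring; the recordings and markers are already part of the planned data collection. Automatic windows are a different and possibly noisier measure, so they should serve only as a sensitivity analysis. If the Week 12 conclusions agree both ways and log-minus-marker times are similar in the two arms, the concern is largely answered. If they differ, the sleep results should be reported with that limitation.

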**Aim 2:** Determine if **Sleep-Opt** will result in improved psychological and behavioral outcomes, including diabetes distress, diabetes self-management behavior, QoL, fatigue, mood, subjective sleep quality compared to the healthy living attention control group. Rationale: Sleep variability and insufficient sleep duration was associated with diabetes distress, poor self-management behavior and reduced QoL. Hypothesis: **Sleep-Opt** will lower diabetes distress, improve self-management behavior and QoL. Approach Assess diabetes distress, self-management behavior, QoL and other patient-reported outcomes (fatigue, mood, sleep quality) at Week 0 (baseline), Week 6 (mid-treatment), Week 12 (end of treatment), post treatment at Week 24 in **Sleep-Opt** compared to a 12-week healthy living attention control. .

**Aim 3:** Determine the contribution of changes in sleep variability and sleep duration during the intervention to changes in glycemic parameters (A1C, glycemic variability, time in range) Rationale: Sleep variability was associated with poor glycemic control and greater glycemic variability in T1D adults. Short sleep was associated with reduced insulin sensitivity in T1D. Hypothesis: Reduction in variability and improved sleep duration will correlate with improvement in glycemic parameters. Approach Analyze the relationship between changes in sleep variability, sleep duration, and glycemic parameters (outlined in Aim 1) after a 12-week **Sleep-Opt** and 12-week healthy living attention control at Week 0 (baseline), week 6 (mid-treatment), Week 12 (end of treatment) and week 24 (post-treatment).

Our long-term goal is to advance the understanding of the potential for sleep optimization as an important component of diabetes care to improve glycemic control and QoL. This goal aligns with and enables the NIDDK strategic plan to support research on the prevention, treatment, and cure of T1D and its complications.

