### C.2 Research plan

#### C.2.1 Proposed study overview.

**Figure 4 and Table 3** illustrate the proposed study. We will enroll up to 300 non-shift-working adults aged 18-65 years with a clinical diagnosis of T1D for at least one year who report habitual sleep variability (> 1 hour variation in sleep onset or wake up time/week) or insufficient sleep duration < 6.5 h/night during work- or weekdays. After informed consent is obtained, participants will have a baseline assessment during a 1-week run-in phase. Subjective sleep and objective sleep assessment by wrist actigraphy will be performed to confirm eligibility. Eligible participants will then be randomized to either a Sleep-Opt or healthy living attention control group for 12 weeks. At baseline, diabetes distress, diabetes self-management behavior, quality of life, self-reported fatigue, sleep quality, mood, anxiety, fear of hypoglycemia, daytime sleepiness, and anxiety will be assessed. Glycemic assessments will be performed by A1C, and 1-week continuous glucose monitoring (CGM). At 6 weeks (mid-program) and 12 weeks (end of intervention period), these assessments will be repeated to evaluate the effects of the intervention. At the 24-week follow-up visit, the same assessments will evaluate the program's sustainability.

[figure not shown]

Table 3. Study Overview		Actigraphy	A1C	CGM	Questionnaires
	Baseline week 0		X	X	X
Mid-intervention	Week 6	X	X	X	X
Intervention completion	Week 12	X	X	X	X
Follow-Up	Week 24	X	X	X	X

**C.2.2 Setting:** The study will take place at subjects' home. We will mail study materials and schedule videoconferences for orientation to the study procedures and instruct subjects how to use the study devices.

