**C.2.9.c Secondary outcomes: Diabetes distress, self-management behavior, quality of life.** Diabetes distress will be measured with the Type 1 Diabetes Distress Scale. This 28-item, 6-point Likert scale measures 7 subscales (powerlessness, management distress, hypoglycemia distress, negative social perceptions, eating distress, physician distress, and friend/family distress) as well as provides an overall total distress scale score. Self-management behavior will be measured with the Diabetes Self-Management Questionnaire-Revised (DSMQ-R). This 27-item, 4-point Likert scale measures aspects of self-management behavior and has questions that are specific to those using rapid-acting insulin. Quality of life will be measured with the Diabetes Quality of Life Scale (DQOL), a 46-item, 5-point Likert scale that measures 4 subscales (satisfaction, impact, social/vocational worry and diabetes-related worry). The scales chosen have strong psychometric properties and have been validated in T1D populations.

**C.2.9.d Important patient-related variables.** Self-efficacy, anxiety, fear of hypoglycemia, mood, fatigue, sleep quality, and daytime sleepiness will be measured with validated instruments: Self-Efficacy for Diabetes Scale, General Anxiety Disorder – 7-item (GAD-7), Hypoglycemia Fear Scale II, Center for Epidemiological Studies Depression Scale (CES-D), PROMIS Fatigue Scale, Pittsburgh Sleep Quality Index, and Epworth Sleepiness Scale. Food intake and timing will be measured by 24-hour dietary recall. Because menopausal status can affect sleep, we will use the STRAW+10 (Stages of Reproductive Aging Workshop+10) criteria for staging menopause for women aged 40 and over. Physical activity will be obtained by activity counts from actigraphy recordings.

Table 6 Measures		
Variables	Measures	Frequency
Demographic, health, and literacy information, caffeine and sleep aid use	Demographic, health questionnaire, menopausal status, Clark Scale, Health Literacy Screener (Newest Vital Sign),  Menopausal status (STRAW+10 in women $\geq 40$ years  ), caffeine, sleep aid use	Week 0
Subjective sleep indices	Sleep quality (Pittsburgh Sleep Quality Index),  Epworth Sleepiness Scale 	Week 0

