Objective sleep Indices	Sleep duration, sleep efficiency, sleep variability, sleep and wake timing (Respironics Actiwatch Spectrum Plus®). Confirmed with sleep diary (bedtime, disruptions, wake time).	Weeks 0, 6, 12, 24
Primary measures: Glycemic Indices Glycemic control Glycemic variability	A1C CGM (Abbott Libre®; or Dexcom®): glucose variability: coefficient of variation (CV%), time spent in range 	Weeks 0, 6, 12, 24
Secondary measures: Diabetes distress Diabetes Self-Management Quality of life	T1D Diabetes Distress Scale   Self-Management Questionnaire-R  Diabetes Quality of Life Scale (DQOL) 	Weeks 0, 6, 12, 24
Important Patient-Related Variables	Self-Efficacy for Diabetes Scale,  General Anxiety Disorder – 7-item (GAD-7),  Hypoglycemia Fear Scale II,  Center for Epidemiological Studies Depression Scale	Weeks 0, 6, 12, 24

	(CES-D),  PROMIS Fatigue Scale,  24-hour dietary recall, activity counts from actigraphy recordings.	
Participant Engagement	Number of sessions attended, length of coaching sessions, lessons viewed, Fitbit usage	Weeks 1-12

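### Table 6 schedules the Pittsburgh Sleep Quality Index and the Epworth scale at Week 0 only, whereas Aim 2 (for sleep quality) and C.2.1 (for both) repeat them after baseline

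*Combined protocol and SAP*

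**What the plan says.** Table 6 (section C.2.9) is the only place in the document that sets each instrument against its visits. Its row for subjective sleep contains "Sleep quality (Pittsburgh Sleep Quality Index") and the Epworth Sleepiness Scale, with frequency Week 0. A separate row, headed "Important Patient-Related Variables", has frequency Weeks 0, 6, 12 and 24 and contains neither scale.

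Other sections describe a different schedule:

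- **Specific Aims, Aim 2** makes subjective sleep quality a between-arm comparison and schedules "fatigue, mood, sleep quality) at Week 0 (baseline), Week 6 (mid-treatment), Week 12 (end of treatment), post treatment at Week 24".
- **C.2.1** says that at baseline "self-reported fatigue, sleep quality, mood, anxiety, fear of hypoglycemia, daytime sleepiness, and anxiety will be assessed". It continues: "At 6 weeks (mid-program) and 12 weeks (end of intervention period), these assessments will be repeated to evaluate the effects of the intervention". For the last visit it says "At the 24-week follow-up visit, the same assessments will evaluate" whether the effect lasts.
- **C.2.1, "Table 3. Study Overview"** marks questionnaires at all four visits.
- **C.2.9.d** treats the constructs as one group: "Self-efficacy, anxiety, fear of hypoglycemia, mood, fatigue, sleep quality, and daytime sleepiness will be measured with validated instruments".
- **Section 3.1, Study Procedures** places patient-reported outcomes in general at all four visits.

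Section C.2.10 analyses secondary outcomes with the Aim 1 approach, a repeated-measures model of change from baseline with the 12-week contrast as endpoint. The Statistical Analysis Addendum revises multiplicity, missing data, the per-protocol analysis and Aim 3, but leaves the measurement schedule alone.

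**The concern.** A scale given only at baseline can describe the sample or serve as a covariate, but it cannot show an effect of treatment. Sleep quality is a stated Aim 2 outcome, and the Pittsburgh index is the only sleep-quality questionnaire named to measure it. Because Table 6 is the only instrument-by-visit schedule, it is a plausible source for building the visit forms. If it was used that way, the trial would finish without the data for one of its stated comparisons.

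Subjective sleep also matters for interpretation. In the team's pilot (C.1.4) the control group's objective sleep improved while its subjective sleep did not, and the investigators read this as a reactive effect. Without post-baseline Pittsburgh scores, that contrast cannot be examined here.

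**Working it through.** No power or error-rate calculation applies, and the plan states no figure to reproduce. The check sets the texts side by side and then counts.

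**1. Schedule by source**

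| Source | Pittsburgh index (sleep quality) | Epworth (daytime sleepiness) |
|---|---|---|
| Table 6 | Week 0 | Week 0 |
| Aim 2 | Weeks 0, 6, 12, 24 | not named |
| C.2.1 text | baseline, then Weeks 6, 12, 24 | baseline, then Weeks 6, 12, 24 |
| Table 3 | questionnaires at all four visits, no instrument named | same |
| Section 3.1 | patient-reported outcomes at all four visits, no instrument named | same |

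The specific conflict for the Pittsburgh index is with Aim 2 and C.2.1. For the Epworth it is with C.2.1. Table 3 and section 3.1 agree with the repeated schedule but could not establish the conflict alone.

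**2. Is the Table 6 entry an extraction fault?** Probably not. The cell uses the singular Week, as does the demographics row above it. The repeated rows use the plural Weeks followed by four numbers.

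**3. Is it a deliberate baseline-only choice?** Nothing says so. C.2.9.d names seven instruments:

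- at Weeks 0, 6, 12 and 24 in Table 6: 5 (self-efficacy, GAD-7, hypoglycemia fear, CES-D, PROMIS Fatigue), each with 3 of 3 post-baseline visits;
- at Week 0 only: 7 − 5 = 2 (Pittsburgh, Epworth), each with 0 of 3.

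No reason is given for treating these two differently. The pilot's Table 2 reports the Pittsburgh index as a change score (−1.4 versus +5), so the team has measured it after baseline before.

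**4. Does another measure fill the gap?** No.

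- The Insomnia Severity Index is used only at screening (C.2.6.1).
- The sleep diary records bedtime, disruptions and wake time.
- Actigraphic sleep efficiency (C.2.9b) is objective, whereas Aim 2 asks for subjective quality.

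**5. Consequence for the model.** The dependent variable is the value at Week 6, 12 or 24 minus the value at Week 0. With no value at any later week, it is undefined for every participant. Likelihood-based handling, auxiliary variables and imputation all need the outcome to be observed after baseline in some participants, so they cannot recover it.

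**6. Size**

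- If Table 6 is followed, with 120 completers: 120 × 3 = 360 records per scale, and 360 × 2 = 720 for both.
- Upper bound, if all of the up to 170 randomized attended every visit: 170 × 3 = 510 per scale, and 510 × 2 = 1,020 for both.
- If Aim 2 and C.2.1 are followed: 0.

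**The case against.** The strongest reply is that this is a slip in one cell. The aims and the overview both intend repetition, nothing shows that Table 6 governed collection, and the primary outcomes are untouched. That is fair and caps the seriousness. It does not remove the conflict, because the document gives staff two incompatible instructions and no order of precedence.

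Four narrower points deserve an answer.

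- **Epworth.** Aim 2 does not name daytime sleepiness, so that half rests on C.2.1. The repeating sentence there follows directly after the glycemic assessments and names no instrument. The broad reading is the more natural one, but the Epworth case is weaker than the Pittsburgh case. This stands.
- **Tier of outcome.** The Aim 2 paragraph in C.2.10 lists only distress, self-management and quality of life, and C.2.9.c reserves the secondary-outcome label for those three. That makes sleep quality a lower-tier outcome. However, the C.2.10 list is introduced as inclusive, and the Aim 2 objective names subjective sleep quality, so it is not excluded.
- **Partial substitute.** Sleep efficiency by actigraphy is collected at all four visits and described as a sleep-quality measure. It softens the loss but does not replace a patient-reported scale.
- **Record count.** The 360 and 720 figures count absent data, not bias or lost precision, and the analysis set is intention-to-treat rather than 120 completers. Accepted. The more telling figure is 0 of 3 post-baseline visits.

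**Conclusion.** The contradiction is real. Table 6 allows no post-baseline Pittsburgh or Epworth score. Aim 2 requires one at three later visits for sleep quality, and C.2.1 does so for both constructs.

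The consequence depends on which text is followed. Under Table 6, 2 of the 7 instruments in C.2.9.d have no post-baseline data, and the between-arm effect on subjective sleep quality cannot be estimated. Under Aim 2 and C.2.1 the loss is zero and only the table is wrong. The effect on the primary outcomes is nil in both cases.

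This assumes that the Table 6 cell was read correctly from the source and that no instrument outside the document supplies later sleep-quality scores. It should be corrected, but it does not threaten the main conclusions of the trial.

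**What to change.** Change the Table 6 frequency for the Pittsburgh index and the Epworth scale to Weeks 0, 6, 12 and 24, so that it matches Aim 2, C.2.1 and Table 3. If collection has finished, state which schedule was actually used. If only Week 0 was collected, say that the Aim 2 comparison on subjective sleep quality cannot be made, and report both scales as baseline descriptors.

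The cost is one table cell. If the forms were in fact built from Table 6 and collection is still open, add a few minutes of questionnaire time per participant at each of the three later visits, when other questionnaires are already given.
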